### **12.5 Analyses of Pharmacokinetic/Pharmacodynamic Relationships**

Pharmacokinetic-pharmacodynamic correlations may be assessed using scatter plot figures of selected rhPTH pharmacokinetic parameters (such as but not limited to  $AUC_{0-24}$ ,  $C_{max}$ , time above threshold of 17.2 pg/mL, AUC above threshold of 17.2 pg/mL, time above threshold of 25 pg/mL, and AUC above threshold of 25 pg/mL) against time-matched selected pharmacodynamic parameters of serum total calcium and albumin-corrected calcium, phosphate, creatinine, magnesium,  $1,25(OH)_2D_3$  and FGF23 values and selected urine pharmacodynamic parameters. Appropriate correlation or regression analysis may be explored.

### **12.6 Population Pharmacokinetic and Quantitative System Pharmacology Modeling and Simulation**

This will be covered in a separate SAP.

## **13. OTHER ANALYSES**

### **13.1 Quality of Life Analyses**

Not applicable.

### **13.2 Health Economics and Outcomes Research Analyses**

Not applicable.

## **14. INTERIM ANALYSIS**

An interim analysis is planned for this study. A separate Interim Analysis SAP will be developed to describe the interim analysis. At the end of each cohort a safety review will be performed before proceeding to the next cohort. The review will include, at a minimum, the Coordinating Investigator and the Shire Medical Monitors. The requirements for the data presentations to be used for this safety review will be documented separately.

## **15. DATA MONITORING/REVIEW COMMITTEE**

Not applicable, as no data monitoring review is planned for this study.

## **16. COMPUTER METHODS**

Statistical analyses will be performed using Version 9.4 (or newer) of SAS® on a suitably qualified environment.

WinNonlin Phoenix version 6.3 or higher (Pharsight Corporation, Mountain View, California, USA) will be used for calculating pharmacokinetic and pharmacodynamics parameters.

## **17. CHANGES TO ANALYSES SPECIFIED IN PROTOCOL**

There were no changes to the analysis planned in the latest version of the protocol.

## **18. DATA HANDLING CONVENTIONS**

### **18.1 General Data Reporting Conventions**

Continuous variables will be summarized using the following descriptive statistics: n, mean, median, standard deviation, minimum, maximum. Categorical and count variables will be summarized by the number of subjects (n) and the percent of subjects in each category. Percentages will be presented to 1 decimal place.

The rules for the number of decimal places to present data and p-values are listed below:

1. For measures of median and mean, use 1 decimal place beyond those used for the measurement.
2. For measures of standard deviation and standard error, use 2 decimal places beyond those used for the measurement.
3. For measures of minimum and maximum values, use the same number of decimal places as those used for the measurement.
4.  $\geq 5$  is rounded up away from zero, whereas  $< 5$  is rounded down toward zero to account for rounding of negative numbers.
5. For p-values use 3 decimal places.
6. Presentation of p-values, display p-values that would round to 0.000 as  $< 0.001$ .
7. BMI should be rounded to 1 decimal place for reporting.

### **18.2 Derived Efficacy Endpoints**

Not applicable.

### **18.3 Repeated or Unscheduled Assessments of Safety Parameters**

If a subject has repeated assessments before the start of investigational product, then the results from the final assessment made prior to the start of investigational product will be used as baseline. In addition to determination of baseline, unscheduled visits will be included in PCI value determination. However, for all other summaries only scheduled visits will be used.

All assessments (including unscheduled) will be presented in the data listings.

### **18.4 Missing Date of Investigational Product**

Since the investigational products will be administered during in-patient confinement at a CRC, there should not be any missing dates of investigational product.

## **18.5 Missing Date and Time Information for Prior or Concomitant Medications**

For prior or concomitant medications, incomplete (i.e., partially missing) start date and/or stop date will be imputed. When the start date and the stop date are both incomplete for a subject, impute the start date first.

### **18.5.1 Incomplete Start Date and Time**

The following rules will be applied to impute the missing numerical fields. If the stop date is complete and the imputed start date is after the stop date, then the start date will be imputed using the stop date.

#### **Missing day and month**

- If the year of the incomplete start date is the same as the year of the date of the first dose of investigational product, then the day and month of the date of the first dose of investigational product will be assigned to the missing fields
- If the year of the incomplete start date is before the year of the date of the first dose of investigational product, then December 31 will be assigned to the missing fields
- If the year of the incomplete start date is after the year of the date of the first dose of investigational product, then 01 January will be assigned to the missing fields. The exception to this would be if the year of the start date is the same as the year of the treatment period 2 dose, in which case the day and month of the first dose of investigational product in period 2 will be assigned to the missing fields.

#### **Missing month only**

- The day will be treated as missing and both month and day will be replaced according to the above procedure.

#### **Missing day only**

- If the month and year of the incomplete start date are the same as the month and year of the date of the first dose of investigational product, then the day of the date of the first dose of investigational product will be assigned to the missing day
- If either the year is before the year of the date of the first dose of investigational product or if both years are the same but the month is before the month of the date of the first dose of investigational product, then the last day of the month will be assigned to the missing day
- If either the year is after the year of the date of the first dose of investigational product or if both years are the same but the month is after the month of the date of the first dose of investigational product, then the first day of the month will be assigned to the missing day. The exception to this would be if the month of the start date is the same as the month of the treatment period 2 dose, in which case the day of the first dose of investigational product in period 2 will be assigned to the missing fields.

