### 7.3.2.3 Adverse Event Collection

At each study visit, subjects will be questioned in a general way to ascertain if AEs have occurred since the previous visit (eg, "Have you had any health problems since your last visit?"). Adverse events are collected from the time informed consent is signed. (Please refer to [Section 8](#), Adverse and Serious Adverse Events Assessment.)

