**Table 2: Schedule of Assessments**

Study Visit	Screening		Predose Assessment		Treatment Period 1		Washout	Predose Assessment		Treatment Period 2		Follow-up
	Admin.	Clinical	TP1, D-2	TP1, D-1	TP1, D1	TP1, D2	W a,b	TP2, D-2	TP2, D-1	TP2, D1	TP2, D2	FU
Study Relative Day/ Study Procedures	-120 to -03	-28 to -03	-2	-1	1	2		-2	-1	1	2	Follow-up c
medication t												
Administration of usual supplemental oral calcium and active vitamin D		X	X	X			X	X	X			X
Withhold supplemental oral calcium and active vitamin D s					X t					X t		
Administration of supplemental oral calcium only (no active vitamin D) u					X v					X v		

a Washout period should be ≥5 days (ie, 120 hours) and ≤30 days between first dose of each treatment period (whether dosing regimen is BID or QD).

b The investigator may elect to keep the subject in-clinic for the duration of the study, if the washout period is short (eg, 120-172 hours) and/or there are any safety concerns, and provided that there is a minimum washout of ≥120 hours between administration of IP in each treatment period.

c A follow-up visit must be completed 30±2 days after the last dose of IP.

d If applicable.

e Review and update medical history and re-confirm eligibility.

f In the event a subject is prematurely discontinued from the study, every attempt should be made to complete these assessments.

g The safety blood and urine assessments (Period 1 and Period 2), pregnancy test (for all females, Period 2), physical exam (Period 2), and weight (Period 2) should be collected after the scheduled serial PK and PD assessments have been completed on this study day, and prior to discharging the subject from the Clinical Research Center.

h Randomization will occur prior to administration of IP at Treatment Period 1, Day 1 only after all eligibility criteria have been confirmed/re-confirmed.

i Vital sign measurements should be collected in the supine position at each time point.

j See **Error! Not a valid bookmark self-reference.**, Table 3, and Table 4 for detailed collection time points.

k Weight measurement only.

l ECGs will be performed in triplicate measurement at each time point.

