### 11.1 Adverse Events

Adverse events will be coded using Version 19.0 or newer of MedDRA.

An AE (classified by preferred term) that occurs during the study will be considered a TEAE if it has a start date/time on or after the first dose of investigational product or if it has a start date before the date of the first dose of investigational product, but increases in severity on or after the date/time of the first dose of investigational product. If more than 1 AE with the same preferred term is reported before the date of the first dose of investigational product, then the AE with the greatest severity will be used as the benchmark for comparison to the AEs occurring during the study under the preferred term. An AE that occurs more than 5 days (120 hours) after the last dose of investigational product will not be counted as a TEAE.

Adverse events will be assigned to a treatment as follows. If the onset date of the AE is after first dose in Period 1, but prior to first dose in Period 2, and is  $\leq 5$  days after the date of last dose in Period 1 it will be counted as a Period 1 AE. If the onset date of the AE is after first dose in Period 2, and is  $\leq 5$  days after the date of last dose in Period 2 it will be counted as a Period 2 AE. Period 1 AEs will be assigned to the treatment received in Period 1, and Period 2 AEs will be assigned to the treatment received in Period 2. AEs with onset date  $> 5$  days after the last dose in Period 1 and prior to the first dose in Period 2 will be counted as a Washout AE, not assigned to a treatment, and not considered a TEAE. AEs with onset date  $> 5$  days after the last dose in Period 2 will be counted as a Follow-up AE, not assigned to a treatment, and not considered a TEAE.

When summarizing non-TEAEs by treatment, AEs occurring prior to first dose in Period 1 will be excluded, and other non-TEAEs will be assigned to the last treatment received.

An overall summary of the number of subjects with AEs will be presented by treatment and overall, including the number and percentage of subjects with any AEs, serious AEs, AEs related to investigational product, AEs leading to discontinuation of investigational product, severe AEs, and deaths. The number and percentage of subjects with TEAEs and non-TEAEs will be presented for the same categories.

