### 18.6.1 Incomplete Start Date

Follow same rules as in Section 18.5.1.

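### When both first doses fall in one calendar month or year, SAP 18.5.1 gives partially dated AEs to the Period 1 treatment; its stop-date fallback can also turn a possible Period 1 TEAE into a Washout AE

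*SAP*

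**What the plan says.** SAP 18.6.1 sends incomplete AE onset dates to the medication rules: "Follow same rules as in Section 18.5.1". Section 18.5.1 sorts a date with the day missing into three cases.

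- **Known month equals the first-dose month:** "then the day of the date of the first dose of investigational product will be assigned to the missing day". The location of the Period 2 dose is not examined.
- **Known month is earlier:** the last day of that month.
- **Known month is later:** the first day of that month, except that the Period 2 dose day is used "if the month of the start date is the same as the month of the treatment period 2 dose".

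With day and month both missing, the structure is the same by year. The exception, "if the year of the start date is the same as the year of the treatment period 2 dose", again sits under the later-year bullet.

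A fallback covers an imputed start that falls after a complete stop date: "then the start date will be imputed using the stop date".

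Section 11.1 then classifies the AE by onset. An onset from the Period 1 first dose to 5 days after the last Period 1 dose, and before Period 2 dosing, counts for Period 1, and "Period 1 AEs will be assigned to the treatment received in Period 1". A later onset before Period 2 dosing is a Washout AE, which is neither a TEAE nor assigned to a treatment. Section 11.1 also repeats the summaries for non-TEAEs, under the last treatment received.

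**The concern.** The SAP authors meant to deal with Period 2, since they wrote an exception for it. The exception can be reached only if a month (or year) ends between the two first doses. Otherwise an AE that began after Period 2 dosing is dated to Period 1 and counted under the other regimen.

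The fallback creates a second problem. Where the exception does operate, it may place onset after a known stop date. Onset then moves to the stop date, the latest possible day, which can lie outside the 5-day window although an onset inside it was equally compatible with the record.

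At stake are the by-treatment TEAE tables, including those for hypocalcemia, hypercalcemia and hypercalciuria. Partial dates are plausible for events between stays, because at each visit "subjects will be questioned in a general way to ascertain if AEs have occurred since the previous visit".

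**Working it through.** **Inputs.** The gap between first doses is given in SAP Table 2: "Washout period should be ≥5 days (ie, 120 hours) and ≤30 days between first dose of each treatment period". The TEAE window is 5 days after the last dose (SAP 11.1). Both doses of a twice-daily day fall on one date, so I count in whole days. The documents give no distribution of dose dates or gaps. I assume Period 1 dates uniform over a 365-day year and, for averages, gaps uniform over 5-30 days and onsets uniform over days. The documents state no figure on this point, so there is none to reproduce.

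**1. How often the exception is unreachable.** With L the month length and g the gap:

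P(same month) = Σ over months of max(0, L − g) / 365

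P(same year) = 1 − g/365

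- g = 5: (365 − 60)/365 = 305/365 = 83.6%
- g = 14: (365 − 168)/365 = 197/365 = 54.0%
- g = 21: (365 − 252)/365 = 113/365 = 31.0%
- g = 30: only the seven 31-day months contribute, so 7/365 = 1.9%

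**2. How often a true Period 2 TEAE is dated to Period 1.** With the day missing, this is the average of P(same month) at gaps g + k for k = 0 to 5. For g = 5: (305 + 293 + 281 + 269 + 257 + 245)/6 = 275, and 275/365 = 75.3%.

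| Gap (days) | Doses in same month | Period 2 TEAE dated to Period 1, day missing | Doses in same year | Period 2 TEAE dated to Period 1, day and month missing |
|---|---|---|---|---|
| 5 | 83.6% | 75.3% | 98.6% | 97.9% |
| 14 | 54.0% | 45.8% | 96.2% | 95.5% |
| 21 | 31.0% | 22.7% | 94.2% | 93.6% |
| 30 | 1.9% | 0.3% | 91.8% | 91.1% |
| Mean, 5-30 | 42.5% | 34.9% | 95.2% | 94.5% |

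Example: doses on 3 and 17 March, true onset 18 March, recorded only as March. Imputed onset is 3 March, so the event goes to the Period 1 treatment.

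**3. Error in the other direction.** If the Period 1 dose is in the last 5 days of a month, the Period 2 dose is in the next month and there is no stop date, a Period 1 TEAE dated only to that next month moves to Period 2. On average this affects 8.1% of true Period 1 TEAEs with the day missing.

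**4. Stop-date fallback.** I read it as start = stop. Take doses on 29 June and 20 July, and an AE recorded as July that stopped on 10 July. The exception gives 20 July, which is after the stop, so onset becomes 10 July. That is 11 days after the Period 1 dose, hence a Washout AE. An onset on 1-4 July would have been within 5 days of 29 June. Over all permitted gaps, dose dates and compatible stop dates, this occurs in about 4.5% of true Period 1 TEAE onset/stop combinations with the day missing, and only when the Period 1 dose is in the last 5 days of a month. No true Period 2 TEAE loses TEAE status this way.

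**5. Weight of one event.** Treatments A, C, D and F each have one cohort: 1/8 = 12.5 points. B and E each span two: 1/16 = 6.25 points.

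**The case against.** A reader might infer that most partially dated AEs go to Period 1. The documents do not support that in general. It holds when day and month are both missing, which is unlikely when clinical participation lasts about 90 days. With only the day missing, a shared month is the majority case only for gaps up to 15 days (50.7%), and more than half of true Period 2 TEAEs are misdated only for gaps up to 12 days (52.3%). Actual gaps are not given.

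A reader might also infer that the fallback removes an event from the tables altogether. It does not. Under Section 11.1 the event appears in the non-TEAE tables under the last treatment received, which in the example is the Period 1 treatment. It also appears in the combined special-interest table where relevant, and in the listings. It leaves only the TEAE tables.

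The strongest practical objection is that partial dates should be rare. Subjects are confined from Day -2 to Day 2 of each period (Protocol 3.1), may stay in clinic through a short washout, and CRF entry is expected within about 3 business days (Protocol 9.1). The highest same-month shares belong to short gaps, where onset dates are easiest to establish. This limits the size of the problem but does not make the rule correct.

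Reading the fallback as start = stop is an interpretation. Section 18.5.2 says outright that an imputed stop is set equal to the start, while 18.5.1 is looser. If another date was meant, the SAP should state it.

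Finally, the analyses are descriptive (SAP 2.5, 2.6), and the same-month default preserves TEAE status. Both points stand. With balanced sequences the misattribution blurs the BID-QD contrast, and the documents give no ground for claiming a bias toward either regimen.

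**Conclusion.** The point holds as a minor defect in a stated rule. The Period 2 exception in 18.5.1 cannot operate unless a month or year ends between the first doses, so same-month or same-year partial onsets go to the Period 1 treatment regardless of when they were reported. The same-month share runs from 84% at a 5-day gap to 2% at 30 days, with a mean of 42.5% under uniform dates and gaps; the same-year share is 92-99%. Separately, the exception combined with the fallback can reclassify a possible Period 1 TEAE as a Washout AE, in a narrow calendar setting and on the start = stop reading. That runs against SAP 18.7 and 18.8, which take the cautious value for missing severity and causality after first dosing.

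The number of partially dated AEs is not in the documents and is probably small. The 12.5-point weight of one event should not be read across all six treatments; for B and E it is about 6 points.

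**What to change.** For AEs only, keep the existing bullets when the known month or year is before that of the first dose or after that of the Period 2 dose. Otherwise:

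- **(a)** If the known month or year contains the Period 2 first dose and the event is not known to have stopped before that dose, impute onset to the first dose of the period in which the AE was first reported. If it was first reported in Period 1 or washout and the known month is after the Period 1 dose month, use the first day of the known month.
- **(b)** If the event stopped before the Period 2 first dose, impute onset as the later of the Period 1 first dose and the first day of the known month or year. Use the stop date only if it precedes that imputed date.

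If the reporting period is unknown, keep the current default and flag the event in the listing. Any remaining case, such as an AE dated to the Period 1 month that continues past a Period 2 dose in the next month, also keeps the current rule.

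The March example, if first reported after 17 March, then goes to Period 2. The July example becomes 1 July, a Period 1 TEAE. Retaining the pre-dose bullets matters: without them, step (b) would turn an AE dated May, with a Period 1 dose on 15 June and a stop on 20 June, into a TEAE.

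The cost is SAP wording and slightly more programming. A few events of uncertain onset will remain as TEAEs.

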#### **Missing/Incomplete Time**

If the time is missing and the date is complete and is the same as the date of the first dose of investigational product in either period, or the date is imputed to be one of these dates, then

the time will be set to the time of the first dose of investigational product on that day. Otherwise, missing times will be imputed as 00:00.

If the minutes are given but the hour is not, then the time will be regarded as completely missing and handled as above. If the hour is given but the minutes are not, then if the hour is the same as the hour of a dose of investigational product on that day, then the minutes of that dose of investigational product will be assigned to the missing fields. Otherwise 00 will be assigned to the missing minutes.

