During Treatments A, B and C, supplemental oral calcium and active vitamin D will be withheld starting on Day 1 (pre-dose), through the completion of all study procedures on Day 2 for both the once-daily and twice-daily dosing regimens. Upon completion of all study procedures on Day 2, subjects will then resume their usual supplemental oral calcium and active vitamin D at their next usual daily schedule.

During Treatments D, E and F, subjects will take their usual dose of supplemental oral calcium (but withhold active vitamin D) in the morning on Day 1, prior to investigational product administration. On Day 2, following the completion of all study procedures, subjects will then re-start their active vitamin D at their next usual daily schedule.

During the washout period, subjects will be instructed to take their usual doses of supplemental oral calcium and active vitamin D.

Any subject who experiences symptoms of hypocalcemia or hypercalcemia may be treated at the investigator's discretion, as per local standards. This may include, but is not limited to, intravenous (IV) calcium and/or fluids.

For all dosing regimens, rhPTH(1-84) will be administered in the morning of Day 1 of each treatment period following an overnight fast of at least 8 hours. Subjects will continue to fast

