### **4.5 Pharmacodynamic Set**

The Pharmacodynamic Analysis Set consists of all enrolled subjects who do not have major protocol violations that affect the validity of the PD results, receive at least 1 dose of rhPTH(1-84) and have at least 1 evaluable post-dose pharmacodynamic value available for 1 dose regimen. Subjects who do not meet the inclusion criterion for hypoparathyroidism will be excluded from the PD set. A listing of subjects excluded from the PD Set along with the reason for exclusion is to be generated. In the event of dosing error, proven or suspected based on PK data (extremely low post-dose PTH concentrations), PD data from the subject for the specific treatment period will be excluded. During treatments A, B, and C, if a subject takes supplemental oral calcium/active vitamin D within 24 hours post the last rhPTH(1-84) dose, PD data from the subject for the specific treatment period will be excluded from summary tables and figures. A listing of excluded PD data along with the reason for exclusion will be generated.

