#### **Missing Time**

- If the time is missing it will be imputed as 23:59.

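### SAP 4.5 does not say how untimed supplement intakes are handled. If SAP 18.5.1's 00:00 imputation is used, an untimed but adherent Day 2 restart wrongly removes that PD period from the summaries

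*SAP*

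**What the plan says.** SAP 4.5 sets the exclusion: "During treatments A, B, and C, if a subject takes supplemental oral calcium/active vitamin D within 24 hours post the last rhPTH(1-84) dose", then "PD data from the subject for the specific treatment period will be excluded from summary tables and figures". The excluded data go into a listing with the reason. The section does not mention missing times and does not refer to Section 18.5.

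SAP 18.5 covers prior and concomitant medications, for which "incomplete (i.e., partially missing) start date and/or stop date will be imputed". Protocol 5.2 has calcium and vitamin D recorded as concomitant medication, so they come under these rules. For an untimed start on the date of a period's first dose, SAP 18.5.1 says "the time will be set to the time of the first dose of investigational product on that day". For every other date: "Otherwise, missing times will be imputed as 00:00". Nothing limits the analyses in which the imputed value may be used.

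On the restart in Treatments A to C, SAP 2.1 says that once all Day 2 procedures are complete, "subjects will then resume their usual supplemental oral calcium and active vitamin D at their next usual daily schedule". Protocol 3.1 agrees. Footnote t of the schedule of assessments (Protocol Table 1, SAP Table 2) differs: it ends the withholding with Day 1 and has supplements resume on Day 2.

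**The concern.** The 00:00 convention is harmless for deciding whether a medication counts as prior or concomitant. Carried into SAP 4.5, it puts an intake that happened after the PD window inside that window. A subject who kept to the no-calcium condition would then be treated as having broken it because a clock time was not recorded, and valid serum and urinary calcium data for that period would leave the summaries. Those summaries address the primary objective, and each cohort is planned with at least 8 completers.

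If imputed times are not meant to be used in SAP 4.5, the SAP gives no rule for untimed intakes. The decision would then be made in programming or case by case, in an open-label study.

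**Working it through.** The plan states no figure to reproduce, so the check is clock arithmetic.

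**Inputs**
- Last dose: the morning of Day 1 (QD), or 12 h after the morning dose and still on Day 1 (BID), from SAP 2.1. No clock time is given; 06:00 to 11:00 is assumed as a range and 08:00 as the example.
- Last scheduled serial time point: 24 h for QD and 36 h after the first dose for BID (SAP schedule tables). For BID, 36 − 12 = 24, so in both regimens it is 24 h after the last dose, when the SAP 4.5 window closes.
- Imputed time: 00:00 on Day 2. Day 2 is never a first-dose date, because first doses are at least 5 days apart.

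**Formula.** Let f be the first-dose clock time in hours, with 0 < f < 12. The gap from the last dose to 00:00 on Day 2 is 24 − f for QD and 24 − (f + 12) = 12 − f for BID. Both are above 0 and below 24, so the imputed time is inside the window for every morning dose. A minute-by-minute scan of first doses from 00:01 to 11:59 in both regimens (719 × 2 = 1438 combinations) found none outside.

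| First dose | Regimen | Last dose | Gap to 00:00 Day 2 | Window closes on Day 2 | Day 2 hours left after window | Gap to 00:00 Day 3 |
|---|---|---|---|---|---|---|
| 06:00 | QD | 06:00 | 18 h | 06:00 | 18 | 42 h |
| 08:00 | QD | 08:00 | 16 h | 08:00 | 16 | 40 h |
| 11:00 | QD | 11:00 | 13 h | 11:00 | 13 | 37 h |
| 06:00 | BID | 18:00 | 6 h | 18:00 | 6 | 30 h |
| 08:00 | BID | 20:00 | 4 h | 20:00 | 4 | 28 h |
| 11:00 | BID | 23:00 | 1 h | 23:00 | 1 | 25 h |

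A subject following SAP 2.1 restarts at or after window closure. If that restart is dated Day 2 and untimed, 00:00 always misclassifies it. If it is dated Day 3, the imputed time is at least 25 h after the last dose and does no harm. With an 08:00 first dose, an adherent Day 2 restart can fall anywhere in 16 h under QD but only in the last 4 h under BID. QD, which is Treatment B in these cohorts, therefore carries most of the exposure.

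**Cost of one false exclusion**
- Treatment A or C: 1/8 = 12.5% of periods. Pooled Treatment B (8 in Cohort 1 plus 8 in Cohort 2): 1/16 = 6.25%.
- Going from 8 to 7 subjects at the same SD, the standard error of a mean rises by √(8/7) = 1.069, about 7%. The 95% CI half-width, t/√n in SD units, goes from 0.836 to 0.925, a ratio of 1.106, about 11%.

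**A smaller variant.** When the hour is known but the minutes are not, 18.5.1 sets the minutes to 00 unless a dose was given in that hour on that day. A Day 2 restart recorded only as hour 08, after an 08:20 QD dose, becomes 08:00. That is 23 h 40 min after the dose and inside the window. It needs the final procedures and the restart to share one clock hour, so it is an edge case.

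**The case against.** The strongest objection is that SAP 4.5 speaks of a subject taking a supplement, which means an actual intake, and never invokes Section 18.5. The imputation rules read as support for the prior/concomitant classification in SAP 9. This stands: that imputed times drive the exclusion is an inference. It does not remove the problem, because 18.5.1 is the only stated rule for an untimed start and SAP 4.5 offers no other.

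Frequency is the next objection. Protocol 5.2 treats recording of calcium and vitamin D times on Days -1, 1 and 2 as imperative, and subjects are in-house until the last Day 2 assessment. This also stands. The documents give no basis for a rate of missing times, so no expected number of lost periods can be stated.

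Four stronger readings are tempting, and the documents do not support them:
- *Every untimed Day 2 restart is misclassified.* Only adherent ones are. A BID subject who followed footnote t and took calcium at 08:00 on Day 2, after a 20:00 evening dose, would be 12 h after the last dose and correctly excluded under SAP 4.5.
- *An untimed stop causes the same error.* SAP 18.5.2 says "If the time is missing it will be imputed as 23:59", and 23:59 on Day 1 would be inside the window. But an adherent subject's last intake is on Day -1 (SAP 2.1), so the imputed stop is 23:59 on Day -1, before dosing. A stop dated Day 1 may be a real Day 1 intake.
- *The BID/QD comparison loses a pair.* SAP 12.4.5 summarizes PD data descriptively by treatment and day; no paired analysis is specified.
- *The data disappear.* They leave tables and figures but are listed with the reason, so a false exclusion can be seen.

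Cohorts may also be expanded to secure enough data. That could replace lost numbers but would not correct a wrong exclusion.

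**Conclusion.** The concern holds in conditional form. If the time imputed under SAP 18.5.1 is used for the SAP 4.5 exclusion, every adherent but untimed Day 2 restart in Treatments A to C falls inside the 24-hour window, and that PD period wrongly leaves the summary tables and figures. The timing result needs only a morning first dose. That the imputed time is used at all is a literal reading of two rules together, not something the SAP states.

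The cost per event is 6.25% of pooled Treatment B or 12.5% of A or C, assuming 8 completers per cohort. The number of events is unknown and probably small. This is a modest defect in the rules for a primary PD summary, worth correcting because the correction is cheap. Separately, footnote t disagrees with SAP 2.1 and Protocol 3.1 on when supplements resume. That must be reconciled, because it determines which Day 2 intakes count as adherent.

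**What to change.** 1. Add to SAP 4.5 that only recorded intake times trigger this exclusion, and that times imputed under Section 18.5 do not.
2. Before database lock, query against source every calcium or active vitamin D record on Day 1 or Day 2 in Treatments A to C that lacks a complete time.
3. For records still unresolved, present the PD summaries with and without the affected periods. Do not presume that the intake was before or after the window: with the schedule footnote and the design sections in conflict, either presumption could be wrong.
4. Reconcile footnote t in both schedules with SAP 2.1 and Protocol 3.1.

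The cost is one sentence in SAP 4.5, a few data queries, a repeat summary if any record stays unresolved, and the reconciliation of the schedule text. The downside is that a true early intake with no recorded time could stay in the main summary; the repeat summary would show its effect.
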